1.4 Benefit-risk assessment

Treatment with the HDM SLIT-tablet targets the underlying HDM allergy to provide clinical benefit in both HDM AR/C and HDM AA. In general, clinical efficacy is observed after 8 weeks of HDM SLIT-tablet (12 SQ-HDM) treatment. Thus, subjects in this trial may not experience clinical efficacy during the trial period. However, direct impact on subject's daily life is limited due to the short duration of the trial and limited trial related procedures. The safety profile of the HDM SLIT-tablet in the adolescent population is expected to be favourable and in line with the safety profile in the adult population, and supportive of an overall favourable benefit-risk evaluation.

The route of administration for the HDM SLIT-tablet is sublingual: This provides an advantage over subcutaneous injection, as it has a safety profile allowing for at-home administration conditioned that first intake is done during medical supervision. This results in improved convenience for patients and caters to those who have a fear of injections or who cannot set aside time off work or school for frequent doctor's visits over an extended treatment period.

The most prevalent AEs observed with the HDM SLIT-tablet include local allergic reactions in the mouth and throat (e.g. oral pruritus, throat irritation, and mouth oedema) of mild or moderate severity. There is a risk of more significant AEs, such as serious allergic reactions or larger swellings in the oral cavity. The risk of severe swellings in the oral cavity is low and across the adolescent subpopulation included in the HDM SLIT-tablet development programme, no severe local swellings compromising the airways have been reported and no adolescent subjects were treated with adrenaline/epinephrine due to AEs. A single anaphylactic reaction in an adolescent subject in the 12 SQ-HDM group was reported; the event occurred 2 days after IMP discontinuation and was assessed as unrelated to treatment (Matsuoka et al. 2017).

While the risk of systemic allergic reactions applies to both subcutaneous and sublingual AIT, the risk of severe systemic allergic reactions is considered minimised for the HDM SLIT-tablet, as sublingual administration has not been found to result in relevant absorption into the systemic circulation. However, few cases of serious systemic allergic reactions, including anaphylaxis have been reported post marketing and are considered a class effect of AIT. The medical supervision at first IMP intake is therefore an important precaution. In some cases, the serious systemic allergic reaction has occurred at doses subsequent to the initial dosing.

In the present trial, all subjects/legal representatives will be provided with educational information regarding symptoms of local and systemic allergic reactions and treatment, including a written local and systemic allergic reaction emergency plan. Subjects will be medically monitored during the trial and provided with appropriate treatment, if warranted. Subjects can discontinue from the trial at any time without penalty or loss of benefits to which the subject was otherwise entitled, if they find the treatment intolerable, and without giving a reason.

The population in this trial reflects subjects in whom AIT with the HDM SLIT-tablet could be a relevant choice, however due to the limited duration of the treatment in this trial, subjects cannot expect to experience direct clinical benefit from treatment during participation. However, the short duration will ensure that important safety data is collected with minimal impact on subject's daily life. Importantly, trial participation does not constitute an additional risk compared to normal treatment initiation with AIT, e.g. such as the HDM SLIT-tablet.

Participating in this trial allows subjects who are diagnosed with HDM allergy and who are candidates for SLIT-tablet AIT to enroll and experience the benefit from a thorough clinical assessment of their allergy and from starting one form of AIT in a controlled clinical trial setting. In shared decision making with their physician subjects may continue treatment with marketed drug or choose another form of AIT after the end of the trial period.

Further details about specific benefits and risks for treatment with the HDM SLIT-tablet can be found in the accompanying Investigators Brochure (IB)

1.4.1 Considerations regarding COVID-19

Regarding the pandemic of COVID-19, it is important to highlight that subjects' safety is always first priority. Participating in this trial, including receiving treatment with AIT, is not expected to increase subjects' risk of contracting communicable diseases, including COVID-19. The examinations and procedures (e.g. lung function, SPT, blood sampling) included in this trial are of minimal burden to subjects and do not include assessment outside what standard medical evaluation of allergic subjects would include. The risk to subjects with asthma is considered unchanged as only subjects

with well controlled mild to moderate asthma are included. If regional circumstances related to COVID-19 change, local guidance should be followed.

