4.1 Inclusion criteria

Subjects are eligible to be included in the trial only if all of the following criteria apply:

- I1. Written informed consent obtained from subjects' legal representatives before any trial related procedures are performed¹⁸
- I2. Male or female subjects aged ≥ 12 to ≤ 17 years on the screening day (visit 1) and at the FU-TC.
- I3. A clinical history of allergic rhinitis/rhinoconjunctivitis (AR/C) when exposed to HDM (diagnosed by a physician) of 1-year duration or more (with or without asthma) and with allergic rhinitis (AR) symptoms despite having received allergy pharmacotherapy during the previous year prior to screening visit (visit 1)¹⁹
- I4. Positive skin prick test (SPT) to *Dermatophagoides pteronyssinus* and/or *Dermatophagoides farinae* at screening (wheal size of ≥ 3 mm)²⁰
- I5. Lung function measured by Forced expiratory volume in 1 second (FEV₁) $\geq 70\%$ of predicted value²¹ or according to local requirements while on subject's usual asthma medication
- I6. The subject must be willing and able to comply with trial protocol and adhere to IMP treatment

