4.2 Exclusion criteria

Subjects are excluded from the trial if any of the following criteria apply:

- E1. A clinically relevant history of symptomatic perennial AR/C caused by a perennial allergen source, such as animal hair and dander and/or mould to which the subject is exposed during the 28-day treatment period
- E2. A clinically relevant history of symptomatic seasonal AR/C caused by an allergen to which the subject is exposed, and which could potentially overlap with the 28-day treatment period
- E3. A subject who has previously been included in studies with the HDM SLIT-tablet, or otherwise being treated with the marketed HDM SLIT-tablet (e.g. ACARIZAX, ODACTRA)
- E4. Any SLIT or SCIT treatment with *D. pteronyssinus* or *D. farinae* reaching the maintenance dose within the last 5 years. In addition, any SLIT or SCIT treatment with *D. pteronyssinus* or *D. farinae* within the previous 12 months prior to visit 1
- E5. Ongoing treatment with any allergy immunotherapy (AIT) product at screening

¹⁸ Assent from the subject must be obtained according to national requirements.

¹⁹ The investigator should do everything possible to obtain medical records with documentation for HDM allergic rhinitis. If medical records are not available, verbal history from subject/legal representative can be used to fulfil this criterion and this must be documented in the medical records by the investigator

²⁰ If medication that could interfere with the SPT, according to Table 5, has not been washed out and the positive control is <3 mm, the SPT must be performed/repeated after the interfering medication has been washed out and before enrolment

²¹ Lung function will be measured according to the ATS/ERS spirometry recommendations (Reddel et al. 2009). The subjects will be included based on spirometry values measured at the site and reported by the site according to the site's pre-programmed spirometric reference equations. The reference equations and values used should be documented on every pulmonary function report.

- E6. Severe chronic oral inflammation
- E7. A diagnosis or history of eosinophilic oesophagitis
- E8. Systemic immunosuppressive treatment within 3 months prior to screening
- E9. Any clinical deterioration of asthma that resulted in emergency treatment, hospitalisation or treatment with systemic corticosteroids within 3 months prior to first tablet administration (visit 2)

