- E10. Any clinically relevant chronic disease, including malignancy, that in the opinion of the investigator would interfere with the trial evaluations or the safety of the subject
- E11. A history of chronic urticaria (> 6 weeks) and/or chronic angioedema (> 6 weeks) within the last 2 years prior to screening visit that in the opinion of the investigator may constitute an increased safety concern
- E12. A relevant history of systemic allergic reaction e.g. anaphylaxis with cardiorespiratory symptoms, generalised urticaria or severe facial angioedema that in the opinion of the investigator may constitute an increased safety concern
- E13. Active or poorly controlled autoimmune diseases, immune defects, immunodeficiencies, immunosuppression or malignant neoplastic diseases with current disease relevance
- E14. Treatment with an investigational drug within 30 days or 5 half-lives of the drug (whichever is the longest) prior to screening visit
- E15. Known history of allergy, hypersensitivity or intolerance to any of the excipients or active substances of the IMP (except for *D. pteronyssinus* and/or *D. farinae*)
- E16. Female with positive urine pregnancy test, breastfeeding, pregnant or planning to become pregnant within the projected duration of the trial
- E17. Sexually active female of childbearing potential without medically accepted contraceptive method²²
- E18. A business or personal relationship with trial staff or sponsor who is directly involved with the conduct of the trial
- E19. Previously been enrolled into this trial, is participating in this trial at another investigational site or is participating or planning to participate in any other clinical trial during the duration of this trial
- E20. A history or current evidence of any condition, treatment, laboratory values out of range or other circumstance that in the opinion of the investigator are clinically relevant and might expose the subject to risk by participating in the trial, confound the results of the trial, or interfere with the subject's participation for the full duration of the trial

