²² For the purpose of this protocol the following contraceptive methods are considered appropriate: oral contraceptives, trans dermal patches or depot injection of a progestogen drug (starting at least 4 weeks prior to IMP administration); double barrier method: condom or occlusive cap (diaphragm or cervical/vault caps) plus spermicidal agent; intrauterine device (IUD), intrauterine system (IUS), implant, or vaginal ring (placed at least 4 weeks prior to IMP administration); or male partner sterilisation (vasectomy with documentation of azoospermia) prior to the female subject's entry into trial and is the sole sexual partner for that female subject. Sexual abstinence is acceptable as contraceptive if it is true abstinence and in line with the usual lifestyle of the subject. Periodic abstinence (e.g., calendar, ovulation, symptothermal, post-ovulation methods) and withdrawal are not acceptable methods of contraception. However, national requirements regarding contraception should always be followed.

E21. Has a condition or requires treatment that may increase the risk of the subject developing severe adverse reactions after adrenaline/epinephrine administration

E22. Treatment with restricted and prohibited concomitant and previous medication listed in Table 1.

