7 RESTRICTED AND PROHIBITED CONCOMITANT MEDICATION AFTER ENROLMENT

Restricted and prohibited concomitant medications are listed in **Table 1**. For medications that could possibly interfere with SPT performed at screening, please refer to **Table 5**.

All concomitant medications must be appropriately documented in the eCRF. The use of any concomitant medication must relate to the documented medical history, prophylaxis, or an AE of the subject.

The medication listed in **Table 1** is restricted or prohibited.

Table 1 Restricted and prohibited prior and concomitant medications

Product	Time window	Reason
An investigational product other than the IMP	≤ 30 days or 5 half-lives of the product (which ever longest) before visit 2 and until FU-TC	Possible interaction between IMPs. Protect subject's safety. Interferes with safety evaluations
Anti-IgE treatment, e.g. omalizumab	< 130 days or 5 half-lives of the product (which ever longest) prior to visit 2 and until FU-TC	Interferes with safety evaluations

Product	Time window	Reason
Antihistamine, routine use and preventive use to treat anticipated adverse events: - Oral, intravenous, nasal or ocular - Long-acting (astemizole) (antihistamines Pro re nata (when necessary) are permitted for treatment of acute allergic symptoms, see section 11.5)	From visit 2 and until FU-TC ≤ 90 days before visit 2 and until FU-TC	Interferes with safety evaluation Interferes with safety evaluation
Antidepressant medications: - Antidepressant medication with antihistaminic effect (e.g. doxepin, mianserine) - Tricyclic antidepressants (e.g. amitriptyline, clomipramine) - Monoamine oxidase inhibitors (MAOIs)	≤ 14 days before visit 2 and until FU-TC	Interferes with safety evaluation Interferes with safety evaluation Tricyclic antidepressants and MAOIs may potentiate the effect of adrenaline/epinephrine
Antipsychotic medications with antihistaminic effects (e.g. chlorpromazine, levomepromazine, clozapine, olanzapine, tiordazine)	≤ 7 days before visit 2 and until FU-TC	Interferes with safety evaluation
Systemic glucocorticosteroids	≤ 90 days before visit 2 and until FU-TC	Interferes with safety evaluation
High daily dose of inhaled corticosteroids (ICS)	1 months before visit 2	Interferes with safety evaluation

Product	Time window	Reason

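### Section 1.4.1 relies on good asthma control among enrolled subjects, but no eligibility criterion requires it

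*Combined protocol and SAP*

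**What the plan says.** Section 1.4.1, under the COVID-19 heading, draws a risk conclusion from a description of the population: "The risk to subjects with asthma is considered unchanged as only subjects" "with well controlled mild to moderate asthma are included". Two properties are asserted: limited severity and good control.

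The rules that decide who is dosed are in sections 4.1, 4.2 and 7:

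- I3 admits subjects with or without asthma and adds no qualifier on severity or control.
- I5 sets an FEV1 threshold of 70% of predicted, measured on usual asthma medication, with a local alternative.
- E8 excludes "Systemic immunosuppressive treatment within 3 months prior to screening".
- E9 excludes "Any clinical deterioration of asthma that resulted in emergency treatment, hospitalisation or treatment with systemic corticosteroids within 3 months", counted back from visit 2.
- E22 excludes "Treatment with restricted and prohibited concomitant and previous medication listed in Table 1". That table restricts high-dose inhaled steroids, systemic steroids, anti-IgE and other biologics.
- E10 and E20 are general exclusions that rest on the investigator's opinion. E20 covers, among other things, any condition that "might expose the subject to risk by participating in the trial".

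Section 11.5 lets subjects with asthma stay on their controller therapy within these limits. Table 1 allows a leukotriene receptor antagonist started before entry. Section 5.1 requires discontinuation if asthma turns hard to control.

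**The concern.** This is a safety trial in minors. Ethics committees and authorities are told that pandemic-related risk to subjects with asthma is unchanged, and the reason given is a property of the enrolled population. If the entry rules do not secure that property, the reason is only partly true, and some subjects may be dosed whom the protocol says are not in the trial.

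The sponsor also treats control as relevant to safety elsewhere, since section 5.1 makes its loss a ground for stopping. That rule acts on asthma that gets worse. It is not an entry check for asthma that is already poorly controlled at screening.

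**Working it through.** No arithmetic applies, and the plan states no figure on this point. The check sets each rule that touches asthma against the two properties claimed in section 1.4.1.

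| Rule | What it secures | Requires current control? |
|---|---|---|
| I3 (4.1) | Rhinitis history; asthma optional | No |
| I5 (4.1) | Lung function on treatment, a severity proxy | No; FEV1 can be adequate in a symptomatic subject |
| E8 (4.2) | No recent systemic immunosuppression, a severity proxy | No |
| E9 (4.2) | No severe exacerbation in the 3 months before visit 2 | No; milder symptoms and reliever use do not count |
| E22 with Table 1 (4.2, 7) | No high-dose inhaled steroids, systemic steroids or biologics, a severity proxy | No |
| 9.2 | First dose postponed in subjects with asthma who have a relevant infection | No; triggered by infection |
| 9.4 | Treatment may be interrupted for a viral upper airway infection in a subject with asthma | No; acts after the first dose |
| E10, E20 (4.2) | Exclusion if the investigator forms the opinion | Not asked; neither names asthma |

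Step 1: severity. I5, E8 and Table 1 together make severe asthma unlikely to enter, although none of them uses a severity class. This half of the claim is largely supported.

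Step 2: control. No row requires it. The visit schedule in section 10 lists no assessment of asthma symptoms, night waking, reliever use or a control score at visit 1 or visit 2. Section 15.4 summarises baseline asthma status without defining a control classification.

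Step 3: a test case. Take a 14-year-old with frequent asthma symptoms on low- or medium-dose inhaled steroids, with or without an established leukotriene receptor antagonist. FEV1 is at least 70% of predicted, and there was no exacerbation of the E9 kind in the last 3 months. I3, I5, E8, E9 and E22 are all satisfied, and sections 11.5 and 7 let the background treatment continue. Only an E10 or E20 opinion keeps this subject out. Once formed, that opinion makes exclusion mandatory, but nothing in the text directs the investigator to form it about asthma control.

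Step 4: the protocol's own drafting pattern. E11 (chronic urticaria or angioedema) and E12 (past systemic allergic reaction) each name a condition and then ask for the investigator's opinion, although E20 would cover both. E13 refers to poor control for autoimmune disease. Asthma control, on which section 1.4.1 expressly relies, has no named criterion of this kind.

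**The case against.** The strongest reply is that existing provisions already cover most of this. Asthma is a chronic disease, so E10 and E20 apply to it, and section 1.4.1 itself tells investigators which asthma population is intended. The physician has relevant information: asthma history and lung auscultation at screening, and FEV1, medication and eligibility at both visit 1 and visit 2. Section 5.1 speaks of discontinuation from the trial, and section 15.2 counts screening failures as having entered it. A deterioration during screening is therefore arguably covered before dosing. All of this narrows the gap. It does not close it, because no provision asks for control to be judged, and section 5.1 does not reach a subject who was poorly controlled from the start.

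A second reply is that the sentence is about COVID-19. That stands. A reader might infer that the protocol's general argument on the risk of the tablet in asthma collapses. The documents do not support that: the main benefit-risk text in section 1.4 does not use asthma control as a premise.

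A reader might also infer that I5 is weakened by its alternative, "or according to local requirements while on" usual medication. The documents show no local rule looser than 70%, so that is speculation and forms no part of the point.

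Finally, the remedy is itself a matter of judgement, with no instrument or threshold. That is true. What it adds is that control is named and must be considered for each subject with asthma.

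**Conclusion.** The point holds in a limited form. Section 1.4.1 states a population property as fact. The entry rules limit severity by proxy and remove recent severe exacerbations, but they do not require current control. This is a mismatch between a stated safety premise and the eligibility criteria, and it can affect who is dosed.

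Its size is unknown. The number of subjects concerned would be 250 times the share with asthma, times the share of those who are poorly controlled yet meet every asthma-specific rule and are not excluded under E10 or E20. The documents give neither share, so any head count would be pure assumption and none is offered. Nor do the documents show that such subjects face a higher risk from the tablet, and a reader should not infer that they do.

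No endpoint, sample size or analysis changes. The sponsor should make the correction because the premise concerns minors and the remedy is small.

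**What to change.** Add one exclusion criterion to section 4.2: asthma that, in the investigator's judgement, is severe or not well controlled at visit 1 or visit 2, based on the asthma history, FEV1 and medication already collected. Section 11 already has a physician evaluate the criteria, and section 10 already checks eligibility at both visits, so no new test or visit is needed.

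Rewording section 1.4.1 to match the present criteria would be cheaper and would remove the inconsistency. It would also give up the protection stated there and leave unchanged who is dosed, so the added criterion is preferable.

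The cost is a possible substantial amendment, which under section 17.7 needs sign-off and ethics committee and/or authority approval before implementation, across an estimated 20 to 30 sites. Recruitment may slow slightly, by an amount the documents do not allow to be estimated.

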1.5 Ethical considerations

This clinical trial will follow the principles of the Helsinki Declaration 1964 and subsequent amendments and clarifications (World Medical Association 2013). The trial will be approved by local Independent Ethics Committees (IECs) and regulatory authorities before initiation.

The trial is an open-label trial. All participating subjects will receive active treatment. This eliminates the ethical considerations of placebo treatment, as the efficacy of the active treatment is established.

The trial will be conducted in European countries, where the HDM SLIT-tablet is already marketed and reimbursed to the adolescent population. This leaves the trial subjects with the possibility to continue treatment after trial completion.

2 OBJECTIVES AND ENDPOINTS

2.1 Objective

The objective is to evaluate safety and tolerability of the HDM SLIT-tablet in adolescents (12-17 years of age) with 28 days of treatment.

2.2 Primary endpoint

At least one treatment-emergent adverse event (TEAE)

2.3 Secondary endpoints

- At least one solicited TEAE
- At least one IMP-related adverse event (AE)
- At least one treatment-emergent serious adverse event (SAE)

